We consider that the current intervention evaluation merits using an RCT to effectively test the impact of the intervention as the intervention is novel and untested and we therefore do not know if it will be successful or not. The intervention attempts to address the structural drivers of HIV in the presence of multiple contextual factors and we feel there is sufficient equipoise about the impact to warrant an RCT design.

The target population of the intervention are the most marginalised communities in India, who are also the target population of other government led developmental work. We plan to document the effect of the intervention and the contextual changes in both arms to carefully look at the impacts.

Data entry and analysis

The quantitative survey data will be double entered and cleaned using CPro.

Assessing baseline balance

Cluster randomized trials need to balance the design by having identical treatment group means for all variables to be included in the analysis. We expect that the trial will be largely balanced for the reasons that follow, and that any deviation from the balanced design will be assessed during the analysis stage. First, by virtue of its design, the trial has a relatively large number of clusters and individual respondents, which will likely help balance covariates across groups. Secondly, the design also accounted for the geographical unit where the school is located when randomizing the clusters in the trial. Third, as government schools, the schools included in the design are more or less of similar character. Although measures were taken to minimize imbalance, any remaining imbalances at baseline will be addressed as described below.

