We will consider two criteria, first is the criterion of the variance of the treatment effect and the second is a criterion of assessing change in treatment effect as defined as the difference between the crude and adjusted treatment effect. We plan to analyze both the variance of the estimated treatment effect and the extent to which the estimated treatment effect changes by adjusting for covariates (Raab and Butcher, 2001)²¹. The approach that will be used in this trial is to assess the extent to which the adjustment of covariates will affect the estimated treatment effect. If the allocation of treatments to units is imbalanced, it is likely to produce a substantial difference between the unadjusted and adjusted estimates of the treatment effect. Using the following general expressions, which Raab and Butcher (2001) developed, this will be overcome as follows.

The estimate of the treatment effect, without any adjustment for covariates, becomes a difference in weighted cluster means of the outcome as;

$$Y_{..2} - Y_{..1} = \frac{\sum_{j:t=2} w_j y_{.j}}{\sum_{j:t=2} w_j} - \frac{\sum_{j:t=1} w_j y_{.j}}{\sum_{j:t=1} w_j}$$

where the weights are $w_j = s^2 m_j / (s^2 + t^2 m_j)$ and s^2 and t^2 are the estimates of between- and within-cluster variances as noted respectively τ^2 and σ^2 , m_j be the number of members in the j th cluster, y_{ij} be the outcome of i th member of the j th cluster and t be the different trial arms (intervention or control) as denoted by 1 or 2.

The variance of the estimated treatment effect can be estimated by

$$s^2 [1/(\sum_{j:t=1} w_j) + 1/(\sum_{j:t=2} w_j)]$$

²¹ Gillian M. Raab, Izzy Butcher (2001), Balance in cluster randomized trials, *Statistics In Medicine*, Statist. Med. 2001; 20:351{365

The study will be estimating the change in treatment effect, when adjusted for the covariates using

$$\sum_{K=1,2,\dots,p} \beta_k (x_{k,2} - x_{k,1})$$

Where β_k is the estimate of regression coefficient for predicting y from the k^{th} covariate and $x_{k,t}$ is the weighted mean of the cluster means for treatment t for the k^{th} covariate, with weights w_j as defined above and p the number of covariates.

Analysis of primary outcomes

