At project completion, we will assess whether, at follow up, there are significant differences between the intervention and control girls in the key indicators of entering 8th standard, completing tenth standard, being married, having sexual debut and entering into sex work. In the course of the analysis we will present simple cluster summaries for the primary outcomes. We will perform statistical tests, using the t-statistic, to assess the significance of and differences observed between the arms.

The final analysis will assess whether the intervention and control schools, adolescent girls and their families significantly differ in terms of the intermediate and short-term outcomes. As recommended by Hayes and Moulton²², given the large number of clusters and because of reasons related to statistical efficiency, individual-level regression methods will be used to test for significant differences in outcomes between intervention and control arms. For each outcome of interest (e.g., the proportion of girls married at the end of the study period, the proportion of girls passing to 10th Standard, etc.), multivariable logistic regression models using generalized estimating equations (GEE)^{23,24} to address clustering at the school level will be estimated. Stata 11 will be used for all analyses. Similar methods will be used to compare short- and medium-term outcomes among SC/ST girls and their families between intervention and control arms.

Qualitative data analysis

The qualitative data will be transcribed and translated into English. Qualitative analysis packages (eg., NVivo9, ATLAS TI) will be used to identify key issues and themes emerging over time. These findings will be used along with the quantitative findings to understand the impact of the intervention.

Addressing confounding factors, selection bias, spill over effect and impact heterogeneity

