The RCT design will reduce problems associated with confounding factors and selection bias, and there is sufficient geographic dispersion of the villages (Figure 1) to minimize spill-over effects. Further, the large sample size will help reduce the risk of missing a true effect. The comparability of the intervention and control samples will be assessed at baseline, and any differences controlled for in the final analysis. Impact heterogeneity will be addressed by examining the intensity of exposure to the intervention among the adolescent girls, their families, boys in the neighbourhood, and the associations between intensity of exposure and the outcomes of interest.

²² Hayes RJ, Moulton LH. Cluster Randomized Trials. Boca Raton: Chapman & Hall; 2009.

²³ Liang KY, Zeger SL. Longitudinal analysis using generalized linear models. *Biometrika* 1986;73:12-22.

²⁴ Zeger SL, Liang KY. Longitudinal data analysis for discrete and continuous outcomes. *Biometrika* 1986;42:121-30

Potential biases (selection, interviewer and recall biases) will be assessed and addressed in the trial as follows:

Selection bias will be largely addressed as a result of the careful process of randomization and selection of subjects. There are chances of selective loss to follow-up which can lead to a bias in the cohort. This is planned to be addressed with negative case analyses to look into reasons for dropout and triangulation of qualitative and quantitative data. The self-selection bias with those adolescent girls and families likely to drop out or refusing to participate is planned to be countered by the trust created by a careful informed consent process.

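### Covariate adjustment is tied to baseline differences seen after randomisation instead of a short fixed prognostic set, and the crude-versus-adjusted comparison is not barred from deciding on adjustment

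*Protocol*

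**What the plan says.** The rule appears in two places in the Protocol.

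- Under 'Addressing confounding factors, selection bias, spill over effect and impact heterogeneity', the two arms are to be compared at baseline, with "any differences controlled for in the final analysis".
- Under 'Assessing baseline balance', which starts from the premise that the arms need equal means on every analysed variable: "any remaining imbalances at baseline will be addressed as described below".

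What follows in the balance section is a comparison of effects. The trial is to "assess the extent to which the adjustment of covariates will affect the estimated treatment effect". The variance of the estimate is named as a further criterion. The change is given as a sum, over all p covariates together, of each regression coefficient for the outcome times the arm difference in that covariate.

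'Analysis of primary outcomes' plans two things. One is unadjusted: "In the course of the analysis we will present simple cluster summaries for the primary outcomes", compared by a t-statistic. The other is "multivariable logistic regression models using generalized estimating equations (GEE") for each outcome of interest. No covariate is named for that model, and no threshold is given for a baseline difference or for a substantial change in effect.

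**The concern.** A protocol may leave its covariate list to the SAP, so the missing list is not the complaint. The complaint is that the protocol states a rule for choosing covariates, which an SAP written to follow it would inherit.

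After randomisation, an observed baseline difference is chance and says nothing about whether the covariate predicts the outcome. Prognostic value is what makes adjustment useful. A rule keyed to differences will usually leave out a prognostic covariate that is balanced, and will sometimes bring in an irrelevant one that is not. The adjusted model then varies with the data instead of being fixed beforehand.

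The change-in-effect formula needs coefficients that predict the outcome, so it can be computed only once outcomes are known. The text does not say that this comparison stays out of the decision to adjust. At stake are the precision of the adjusted analysis and whether its estimate is defined in advance.

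**Working it through.** **1. The protocol's sizing, reproduced.** The unmatched cluster formula is c = 1 + (1.960 + 0.842)² × [p0(1−p0)/m + p1(1−p1)/m + k²(p0² + p1²)] / (p0 − p1)², with m = 28 girls per cluster, two-sided 5% and 80% power. For transition with p0 = 17%, p1 = 11.9% and k = 0.20:

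- sampling part: (0.17×0.83 + 0.119×0.881)/28 = 0.008784
- between-village part: 0.04×(0.0289 + 0.014161) = 0.001722
- c = 1 + 7.849 × 0.010506/0.002601 = 32.7, as printed. For k = 0.15 and 0.25 the results are 30.4 and 35.6, also as printed.

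The sizing assumes an unadjusted t-test, so the adjustment rule does not touch it.

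**2. What an imbalance rule selects.** The protocol gives no cut-off; I assume p < 0.05. Under randomisation each covariate is picked with probability 0.05 whatever its prognostic value. With six candidates the expected number picked is 6 × 0.05 = 0.3, and the chance that none is picked is 0.95⁶ = 0.74 (treating them as independent). The rule therefore comes close to no adjustment.

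**3. Simulation.** 40 villages per arm; linear regression on cluster means; equally prognostic covariates jointly explaining a share R² of cluster-mean variance; effect set at (1.960 + 0.842) × √(2/39) = 0.634 SD, for a nominal unadjusted power of 80%. R² and the number of covariates are assumptions.

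| Covariates | R² | Power, imbalance rule | Power, fixed set |
|---|---|---|---|
| 6 | 0.05 | 78% | 78% |
| 6 | 0.10 | 80% | 81% |
| 6 | 0.20 | 79% | 86% |
| 6 | 0.30 | 81% | 89% |
| 10 | 0.05 | 78% | 76% |

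Repeat runs differ by a point or two. Eight covariates give 80% vs 81% at R² 0.1, 81% vs 88% at 0.3 and 83% vs 96% at 0.5. Type I error under the imbalance rule is about 4–5%, and on the conservative side when the covariates are strongly prognostic.

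**4. Which R² is plausible.** Take the protocol's inputs at k = 0.20.

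- Transition (13% vs 8.71%): between-village variance 0.000979, sampling variance 0.006879; between-village share 0.000979/0.007859 = 12%.
- Retention (30% vs 22.5%): 0.005625 and 0.013728; share 0.005625/0.019353 = 29%.

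Over the protocol's range of k from 0.10 to 0.25 the shares run from 3% to 18% (transition) and from 9% to 39% (retention). If covariates explain 30% of the between-village part only, at k = 0.20, R² is 0.3 × 0.125 = 0.04 to 0.3 × 0.291 = 0.09, where the fixed set gains almost nothing. Higher values need girl-level covariates that also explain differences within villages. That is possible for items such as age or parents' education, but the protocol gives no figure.

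**The case against.** The balance section never says that covariates are chosen by how far they move the treatment effect. Its formula is joint over all covariates, it has no covariate-by-covariate screen or threshold, and it names variance as a further criterion. It reads naturally as a diagnostic. That stands. A reader might infer selection on the change in effect, but the text supports only that such use is not excluded.

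The comparability check is made at baseline and needs no outcome data, and an unadjusted t-test on cluster summaries is planned for the primary outcomes. That also stands: a result free of the rule will exist, and crude results are already to be presented.

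A reader might also infer an inflated false-positive rate. A free choice of the best p-value among crude, fully adjusted and single-covariate models would raise it to about 9–13% in simulation with eight covariates, but the protocol plans no such choice.

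Finally, a reader might suspect that adjusting for cohort 2 baseline differences would remove part of the intervention effect, because that baseline comes a year after cohort 1. The document does not say that attitude or awareness items will be adjusted for, and the timeline shading that would date the start of the intervention is not visible in the text. This supports at most a precaution.

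None of these answers the sentence that ties adjustment to observed differences.

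**Conclusion.** The point holds in limited form. The protocol makes adjustment depend on chance baseline differences and leaves open whether an outcome-based comparison may influence it. The consequences are possible omission of prognostic covariates and an adjusted estimate not fixed in advance. Type I error under mechanical use, the sample size and the unadjusted t-test are not affected.

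The precision at stake runs from nothing at R² 0.05 to about 8 percentage points of power at R² 0.3 with six covariates. A single gain should not be quoted without that range. The figures rest on an assumed p < 0.05 cut-off, equally prognostic covariates and a linear cluster-level model standing in for the logistic GEE. It should be corrected, mainly because correction is cheap and fixes the adjusted analysis in advance; a large gain in power is not assured.

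**What to change.** - Replace the sentence on controlling for differences, and its counterpart under 'Assessing baseline balance', with adjustment of the GEE model for a short fixed set chosen for prognostic value, regardless of observed balance. Candidates are district, cohort, girl's age, SC versus ST, parents' education and devadasi family status. Cohort is known by design and the rest fall under the demographics in Table 4.
- Use the baseline comparison for description only.
- State that the change between crude and adjusted effects is reported as a comparison and not used to choose covariates.
- As a precaution, keep attitude and awareness items out of the list.

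The cost is wording and minor programming, with no new data. The statistical price is a few degrees of freedom, with a slight loss of power if the list is long and weakly prognostic (ten covariates at R² 0.05: 76%, against 78% under the imbalance rule). The list should therefore stay short.

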Appendix 1. *Sabala Project Implementation Design.*

See separate PDF document.

Appendix 2. *Quantitative baseline behavioural questionnaires.*

See separate documents: Girls questionnaire, Families questionnaire, Schools questionnaire.

Appendix 3. Interviewer's Guide for Lifeline studies

Interviewer's Guide for Lifeline

The following is a guide to be used for the case studies using lifeline methods in the *Sabala* (Adolescent girl) programme which Karnataka Health Promotion Trust is implementing as a part of the STRIVE project to support adolescent girls from marginalised communities in northern Karnataka.

The lifeline case study approach provides an opportunity to gain meaningful insight into the lives of participants, and the impact that Sabala is having or has had upon their lives. During annual in-depth interviews you will engage with selected adolescent girls in participatory lifeline mapping to explore events and experiences in her life before and during the intervention period.

Process

1st meeting

The first part of the data collection interview will be introduction to the study and the informed consent procedure. Written consent will be obtained from both the parent (or guardian in case the parent is not available) and the girl. The girl will then be invited to a practice session.

2nd meeting

This will essentially be a training session for the girl to familiarise her with the research technique and the lifeline tool. Mock sessions with the lifelines can be done using examples like a universally known story like the Ramayana or the life of a chicken in their village. The interviewer will continue with imaginary situations until she is convinced that the girl has understood the concept. This can be the forum to provide assurance about confidentiality, anonymity and of being non-judgmental.

The consent for her first life line interview can be taken deciding on a comfortable venue and date.

Introduction to the lifelines

We will be drawing the events and experiences that happen in an individual's life during a period of time with the help of a graph. We list down events according to how people feel about them. Events that make you feel good and happy we will mark in the region above the horizontal line and those you don't feel so good about, below the horizontal line.

I will show you a sample graph here to you. (Show the graph) Have you used these kinds of graphs at school? This graph is about the life of (Sri Rama) in his lifetime. (Explain sample graph). As you can see in this example each person can have different facets of their life and positive or negative events may happen in it across a period of time. Your feelings about the event can range from feeling really terrible or sad about it, in which case we place it at -2, to not feeling good or just sad, in which case it will be somewhat above at -1. You may chose to place events at any place in between. Similarly for events which make you happy. Events that are neither happy nor sad can be place on the line. We can at the end draw lines to connect these dots.

Let us do a practical session about the life of your dog or your chicken. Let us do one example graph and then you can draw on your own. We can use pens of different colours for making out four different sets of events. (Go through a practical discussion of the lifelines created)

Next time we meet we will do a similar exercise representing events in your own life using four colours. I can tell you now how this will work but not to worry – we will do this together next time. We will try to make four different lines using these.

- One line for school in red and for events at school including test marks, assignments, school atmosphere, teasing, ragging, teacher scolding or praising etc.
- One for how you feel about yourself in green in the family atmosphere like happy events in family, praise from parents, visits by relatives and when something good or bad for you life is discussed.
- The third line in blue will denote the schemes that you get from the government through the school with up and downs depicting receipt or completion or difficulties.
- We will also put other important events which are not linked to the lines marked with stars or dots or the stickers here (which one do you like?) anywhere here again according to how you feel about it: positive or negative. These can be anything you like to add marriage or betrothal of close friends, social/cultural event, etc.

(You could give them a sample sheet if they want it, but would let her draw it again in your presence)

When is the most convenient time for the next meeting?

Where do we meet?

(Suggest the place as discussed during the initial meeting involving the parents)

3rd and subsequent meetings

The main interview will be conducted in the place and time suggested by the participant. The mapping will be done by the interviewer and the girl together in a participatory manner with the interviewer marking the events on the paper as indicated by the girl herself and not

directed by the interviewer.

The interviewer will try to explore each lifeline in detail and why the girl perceives the event as positive or negative and how she describes these events. The lifelines will provide cues for the discussion. The conversations will be recorded and transcribed by the interviewers.

- Different lines will be marked different coloured pens to avoid confusion. One sheet of paper will be used to record the lifeline for the year, although the lifeline will be constructed semi annually. The school outcomes line in red can include performance in internal tests, school atmosphere, events of teasing, positive or negative feedback/issues with teachers, etc.
- The schemes line in green may include availing schemes with up and downs depicting receipt or completion or difficulties.
- The family support line in blue may include positive vents like appreciation of parents on performance, pressures from extended family on getting her engaged or married.
- There can also be independent events marked with a star or circle in the positive or negative quadrant along the line depicting events that are not directly linked to lifelines but may be perceived as important event by the girl in her life. This may include marriage or betrothal of close friends, social/cultural event, etc.

Consent for recording will be taken in advance from the girl and her family and also before each set of data collection. At the end of the second session the interviewer will summarise the events lifeline with the help of the girl. In the next set of interviews the previous lifelines could be looked at the end of the session.

Developing the lifelines

We will use the technique we discussed last time to think and discuss about your life.

Step 1: Review of lifeline drawn

Have you tried to draw your lifeline as I suggested last time? (If yes skip to step 3. Review with participant and if satisfied move to next step. If not complete then go to step 2. If not drawn, go to step 2.)

Step 2: Listing and drawing

What we will do is list down events according to how you feel about them. Events you feel good and happy about, we will mark in the region above the horizontal line and those you don't feel so good about below the line. Your feelings about the event can range from feeling really terrible or sad about it, in which case we place it at -2, to not feeling good or just sad, in which case it will be somewhat above at -1. You may chose to place events at

any place in between. Similarly for events which make you happy. Events that are neither happy nor sad can be place on the line.

Do you want to mark events yourself? Or would you be interested in pointing out and instructing me to draw? I will show you a sample graph here to you. (Show and explain sample graph)

[figure not shown]
I have pens with four different colours here for making out four different sets of events in your life. We will try to make four different lines using these.

Step 3: Detailing out

We will now go through all the events that you have marked on the lifeline one by one.

Could you tell be why you have marked _____ event here? (pointing out each line and event one after the other)

How did this event affect you? Could you describe your experiences in detail? What are the changes that have happened since the last time we met? (from second meeting onwards)

Step 4: Looking at the future

We will also look at your hopes for the future few months and future years. We can put your hopes for near future in dotted lines on the graph and discuss your progress when we meet next.

Could you tell me where you would wish this line should be moving next? (pointing out to one line after the other)

Step 5: Review

Are you happy with the way your lifeline is looking now? Are there any changes that you would like to make, especially based on what you have spoken in the interview?

Step 6: Reviewing previous lifeline

(For the second interview onwards)

Let us now look at the lifeline you drew last time to see how your life has changed in these months.

(Here the interviewer can look at the key moments and probe for things like “Oh, your sister was having a baby, how is that?” or try to get the changes she perceives in her own words with- “Wow, look how your life has changed in these months.”)

Debrief

Is there anything that you would like to add to the lifeline or any other detail that you would like to speak about?

If you think of anything later that you want to change, or want to add we can do that. You have my phone number and you can feel free to call me and we will talk about the changes you want to make. I will show you the changes when I come to see you again in a few months.

